7.7.1 Other concomitant treatment

Other medication than that described above, which is considered necessary for the patient's safety and wellbeing, may be given at the discretion of the Investigator and recorded in the appropriate sections of the eCRF.

Following the final PFS analysis data cut off for a stratum (either non *HRRm*, *BRCAm* and/or non *BRCAm HRRm*) concomitant medications should be recorded in the patient notes **but not** recorded in the eCRF

In addition, any unplanned diagnostic, therapeutic or surgical procedure performed during the study period must be recorded in the eCRF.

Following the final PFS analysis data cut off for a stratum (either non *HRRm*, *BRCAm* and/or non *BRCAm HRRm*) unplanned diagnostic, therapeutic or surgical procedures should be recorded in the patient notes **but not** recorded in the eCRF.

8. STATISTICAL ANALYSES BY ASTRAZENECA

8.1 Statistical considerations

Statistical analyses will be performed by AstraZeneca or its representatives including CROs. Further details of the statistical analysis will be described in an SAP.

Patient populations related to the study objectives

Statistical analyses will be done for up to 5 patient populations based on the tumour biomarker strata A, B, C.

- “*BRCAm*” = patients from stratum A
- “*HRRm*” = patients from stratum A and patients from stratum B
- “Non *BRCAmHRRm*” = patients from stratum B
- “All” = patients from any stratum
- “Non *HRRm*” = patients from stratum C

Primary statistical analyses comparing PFS based on BICR for each combination treatment arms to olaparib will be conducted for the 3 patient populations *BRCAm*, Non *BRCAm HRRm* and Non *HRRm*.

Comparisons of PFS based on BICR for each of the combination treatment arms to olaparib in the 2 patient populations *HRRm* and All will be conducted as secondary statistical analyses.

Secondary outcome measures will be analysed for the 3 patient populations *BRCAm*, Non *BRCAm HRRm* and Non *HRRm*, except

- OR and OS, which will be analysed for all 5 patient populations
- Tumour and germline mutation status, which will be analysed only for the All patient population
- PK outcome measures, which will be analysed only for the All patient population

RECIST-based primary and secondary outcome measures based on Investigator assessments will also be analysed for sensitivity purposes.

Safety outcome measures and exploratory outcome measures will be analysed for the All patient population, except **CCI** which will be analysed for all 5 patient populations.

Handling of multiplicity

Multiplicity adjustment will be considered within each of the 3 primary patient populations for PFS. The overall alpha for each primary patient population will be 0.2, and a simple Bonferroni adjustment assigns alpha of 0.1 to each of the 2 pairwise treatment arm comparisons to olaparib.

No further adjustments for multiplicity are planned.

Overview of timings of interim and final analyses

For the non *HRRm* population an interim futility analysis will be triggered when 75 patients have been recruited and assessed for at least 8 weeks, in order to assess the proportion of patients with Non Progressive Disease (NPD), based on the Investigator assessment at

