- Patients with documented presence or absence of qualifying mutation(s) in tumour tissue predicted to be deleterious or suspected deleterious in one of **CCI** HRR genes. All patients must provide a formalin-fixed paraffin embedded (FFPE) tumour specimen sample for tissue-based HRR gene panel testing using the clinical trial assay (CTA) known as the Lynparza HRR assay. Tumour tissue samples can be obtained/can originate from either primary tumour (eg, archival breast cancer specimen) or metastatic biopsy. If an archival FFPE sample from the primary tumour is not available for molecular analysis, an FFPE sample from a biopsy of a metastatic lesion, collected following progression on a prior line of therapy, may be used for this testing. The tumour sample will be tested for mutation in **CCI** pre-specified HRR genes. If the test results indicate that the

patient has a qualifying mutation in the breast cancer susceptible genes 1 or 2 (*BRCA1* or *BRCA2*), the patient is eligible for stratum A of the study. If the results indicate that the patient has a qualifying mutation in any of the remaining **CCI** HRR genes **CCI** [REDACTED] and does not have a qualifying mutation in either *BRCA1* or *BRCA2* genes, the patient is eligible for stratum B. If the results indicate that the patient has no detected qualifying mutation in any of the **CCI** HRR genes, the patient is eligible for stratum C. Prospective screening will be implemented to ensure equal patient numbers in each stratum (*BRCAm*, non *BRCA* HRR*m*, and non HRR*m*). Foundation Medicine, Inc. (FMI) will provide the CTA, a novel next generation sequencing (NGS)-based assay, that will be performed as a single laboratory testing service using DNA extracted from FFPE tissue. Patients may be randomised based on a local test verified and validated in line with local regulations, within a GCP laboratory showing a qualifying mutation in any of the **CCI** HRR genes but must provide sufficient tissue sample for retrospective analysis with the FMI test.

Treatment setting

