Approximately 450 patients will be randomised (using randomisation ratio 1:1:1) to olaparib monotherapy, olaparib+ceralasertib or olaparib+AZD1775. Following the closure of the olaparib+AZD1775 arm in April 2019 the total number of patients randomised will be lower (approximately 350 patients).

The randomisation scheme will be stratified based on:

- stratum A: patients with mutations in *BRCA1* or *BRCA2* (*BRCAm*)
- stratum B: patients with mutations in any of the following ^{CCI} genes involved in the HRR pathway (^{CCI}) and no mutation in *BRCA1* and no mutation in *BRCA2*
- stratum C: patients that have no detected tumour mutations in any of the ^{CCI} HRR genes mentioned above.
- tumour biomarker strata A, B, C defined above
- patient's prior platinum-based therapy (no / yes).

The 3 strata will be capped to achieve approximately 150 patients within each stratum (approximately 50 patients per treatment arm). Following the closure of the olaparib+AZD1775 arm, fewer than 50 patient per stratum had been randomised to this arm.

Please refer to the study flow chart (Figure 2).

Figure 2 Study flow chart

[figure not shown]
[figure not shown]

Figure 3 Diagnostic journey

- Note: Stratum A: *BRCAm*, stratum B: non *BRCAm* HRRm stratum C: non HRRm. The AZD1775+olaparib treatment arm was closed following the ISRC meeting on the 17 April 2019.

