
 • BRCAm • Non BRCAm HRRm • Non HRRm 	To compare the efficacy of the combination of ceralasertib+olaparib with the combination of AZD1775+olaparib in terms of 
 • DoR • tumour change 	DoR and tumour change using BICR according to RECIST 1.1 Sensitivity analysis of DoR and tumour change using Investigator assessments according to RECIST 1.1

 • BRCAm • HRRm • Non BRCAm HRRm • All • Non HRRm 	To compare the efficacy of the combination of ceralasertib+olaparib with the combination of AZD1775+olaparib in terms of OS	Time to death for any cause

 • All 	To explore the frequency of and describe the nature of tumour HRR (including BRCA) mutation(s) in tumour samples and to compare this with germline HRR (including BRCA) mutation status	Mutation status of cc1 genes

 • All 	To assess exposure to olaparib ceralasertib and AZD1775 in all patients	C _{min ss}

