Patients must provide a blood sample at screening Part 2 (see Table 3). The sample is requested prior to treatment in order to maximize the probability of detecting CCI where the tumour burden is relatively high. Several samples will be taken during treatment and a last sample will be taken at disease progression (see Table 4 and Table 5) up until the final PFS analysis data cut off for each stratum. **Following the final PFS data cut off for each stratum exploratory sample collection CCI, blood for circulating tumour cells, blood sample for CCI) will stop with the exception of the collection of the CCI sample at the time of disease progression (see Table 6).**

Please refer to the Laboratory Manual for further details of biomarker blood sample collection, shipping and storage.

Other exploratory analysis

Patient blood and tumour samples collected during the course of this study may be used for CCI analysis. Such analysis may include, but is not restricted to:

- CCI
- CCI

- CCI [REDACTED]
- CCI [REDACTED]
- CCI [REDACTED]
- CCI [REDACTED]
- CCI [REDACTED]
- CCI [REDACTED]

Results of these other exploratory analyses will not be reported in the CSR, but may be added in an appendix to the CSR. No formal statistical analysis is planned.

Future research

Patients may consent to future research where their samples may be analysed following the finalisation of the CSR.

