4.2.8.7 Analysis of tumour and germline mutation status of **CC1 genes**

A cross-tabulation summary of the tissue HRR mutation status (Positive, Negative, Invalid, Not Tested) versus the plasma HRR mutation status (Positive, Negative, Invalid, Not Tested) for each mutation type at Baseline will be produced for all screened subjects with both tumour and plasma samples analysed.

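### Tumour HRR mutation frequency is assigned to two different populations, both shaped largely by the stratum caps, so neither estimates the frequency among tested patients

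*Protocol*

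**What the plan says.** **Objective.** Protocol 2.2 lists, for the All population, a secondary objective that begins "To explore the frequency of and describe the nature of tumour HRR"; it also asks for a comparison with germline status.

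**Population in the protocol.** Section 8.1 assigns this outcome as follows: "Tumour and germline mutation status, which will be analysed only for the All patient population". The same section defines All as "patients from any stratum". Section 8.5 assigns patients to populations by the values entered at randomisation, so All means randomised patients.

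**How that population is composed.** The synopsis (target patient population, biomarker selection) says "Prospective screening will be implemented to ensure equal patient numbers in each stratum". Section 1.4 adds "The 3 strata will be capped to achieve approximately 150 patients within each stratum".

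**Population in the SAP.** Section 4.1.8 repeats the restriction to All. Section 4.2.8.7 instead describes a table of tissue status against plasma status that "will be produced for all screened subjects with both tumour and plasma samples analysed". The methods table in 4.2.7 carries both labels: its population column says All and its method column says screened subjects with both samples. Output T 11.2.5.1 is likewise listed under All but titled for all screened patients. Section 6, on changes from the protocol, reads as not applicable.

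**Timing of the samples.** Under Protocol 1.4 and 5.7, tumour tissue is sent for central testing at Screening Part 1. On blood, section 5.7 says "Patients must provide a blood sample at screening Part 2 (see Table 3". Table 2, the Part 1 schedule, lists no blood sample for mutation testing.

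**The concern.** A frequency needs a denominator that was not chosen by the result being counted. Here both candidate denominators were.

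In the randomised set, the ratio of mutated to non-mutated patients is largely a recruitment target. In the SAP's matched-sample set, a patient must reach Screening Part 2 to have plasma, and the biomarker result, with the state of the strata at that time, decides who gets that far. Patients without a qualifying mutation are eligible only until stratum C closes (Protocol 5.7), and stratum C pauses at 75 patients for the futility analysis (Protocol 3.5 and 8.1). On the other side, patients with a known qualifying local mutation can enter on that result (Protocol 1.4 and inclusion criterion 6).

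What is at stake is the frequency part of one secondary objective. No test, alpha or stopping rule depends on it. A share produced by the caps could nevertheless be read as a property of the tested patients.

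**Working it through.** **1. Design figures.** The plan's own total is 3 strata × 3 arms × 50 = 450, or 150 per stratum. This matches Protocol 8.2 and 1.4.

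**2. Mutated share in All, full design.** Share = (A + B) / (A + B + C) = 300 / 450 = 66.7%, if all strata fill.

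**3. Mutated share in All at about 350 patients.** The two open arms contribute 2 × 3 × 50 = 300: 200 in A and B, 100 in C. The closed AZD1775+olaparib arm contributes 350 − 300 = 50. With x of those 50 in A or B, share = (200 + x) / 350.

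| x | Mutated share |
|---|---|
| 0 | 57.1% |
| 25 | 64.3% |
| 50 | 71.4% |

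The middle row is an inference. A futility trigger of 75 at 1:1:1 puts about 25 closed-arm patients in stratum C, leaving 25 for A and B. The documents do not give the split.

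**4. If stratum B does not fill (three-arm design).** Share = (150 + B) / (300 + B). B = 100 gives 62.5%; B = 50 gives 57.1%.

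**5. The SAP's matched-sample set.** Suppose everyone reaching Part 2 has both samples analysed, all strata fill to 150, and a fraction fail screening at Part 2: f₁ of mutated and f₂ of non-mutated patients (assumed values). The share is [300/(1 − f₁)] / [300/(1 − f₁) + 150/(1 − f₂)].

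| f₁ | f₂ | Mutated share |
|---|---|---|
| 20% | 20% | 66.7% |
| 10% | 30% | 60.9% |
| 30% | 10% | 72.0% |

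The true frequency appears in none of these expressions.

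**6. Who is lost before plasma (illustration).** Assume true frequencies of 15% BRCAm and 10% non BRCAm HRRm, all patients tested centrally, and no other losses. Filling stratum B needs 150 / 0.10 = 1,500 tests. Of these, 0.75 × 1,500 = 1,125 are non-mutated, against 150 places in stratum C. The frequency among those tested is 25%; the randomised set shows 66.7%.

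**7. How the error depends on the true value.** Taking 64.3% from step 3, the ratio to an assumed true frequency is:

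| Assumed true frequency | Ratio |
|---|---|
| 15% | 4.3 |
| 25% | 2.6 |
| 35% | 1.8 |
| 50% | 1.3 |

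These frequencies are assumptions. The share of sporadic TNBC with defective HR quoted in Protocol 1.1.1 rests on reduced BRCA1 expression and promoter methylation, so it is not a frequency of qualifying mutations.

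**8. Whether weighting repairs it.** Protocol 8.5.2 calls for weighted analyses in combined populations, but the formulas in Protocol 8.5.1 and SAP 4.2.8.1 combine log hazard ratios. Applied to mutated share, the weights give w_A × 1 + w_B × 1 + w_C × 0 = w_A + w_B, which only returns the weights put in.

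**The case against.** The best defence is that the SAP sets the details and its output rows name screened subjects, so no table of randomised patients giving a mutated share is specified. The one planned output is a cross-tabulation by mutation type, which serves concordance. The objective is exploratory, the equal strata are openly stated, and the caps act between strata, so they do not fix the BRCA1 to BRCA2 split or the gene mix within stratum B. The sponsor also already plans to use screening records to estimate the population mix for the weights.

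Much of this stands. A reader might infer that the trial will report a frequency of about two thirds whatever the truth is. The documents do not support that: it would need an unweighted table of randomised patients with every stratum filled. A reader might also infer a 2- to 4-fold overstatement, but that requires a true frequency of about 15% to 30%, which appears nowhere in the documents. If T 11.2.5.1 were read as every patient tested at Part 1, most of the problem would disappear.

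What does not stand is that the SAP settles the matter. Sections 4.1.8 and 4.2.7 still say All, and 4.2.8.7 requires plasma, which brings the caps back. A concordance table also does not answer the frequency part of the objective.

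One further objection bears on the remedy. Patients with a known local mutation skip prospective central testing (Protocol 1.4), so the prospectively tested set is depleted of known carriers and may read somewhat low. That is correct and has to be stated with the result.

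**Conclusion.** The point holds as a mismatch of populations, neither of which can estimate frequency among tested patients. Protocol 8.1 and SAP 4.1.8 say All; SAP 4.2.8.7 says screened subjects with both samples; SAP section 6 acknowledges no difference. In the randomised set the mutated share would be about 57% to 71%, assuming about 350 patients, 50 per open arm per stratum and about 50 in the closed arm. In the SAP's set the share is also shaped largely by the caps, because plasma is first collected at Part 2.

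The size of the resulting error cannot be stated without the true frequency. Both documents expect the non HRRm population to enrol fastest. If that reflects the natural mix, stratum C exceeds one third and the mutated share is below two thirds, but this gives a direction relative to the full design and no magnitude. The consequence is confined to one descriptive secondary objective; the primary PFS comparisons are unaffected.

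**What to change.** - Name one population for tumour HRR mutation frequency in both documents, and record the change in SAP section 6.
- Report frequency, overall and by gene, among all patients with a valid prospective central Lynparza HRR result at Screening Part 1, whether or not plasma was analysed.
- Show patients entering on a known local mutation separately, and give the overall figure with and without them. State that the prospectively tested set is depleted of known carriers, so its figure may be somewhat low.
- Keep the tissue-by-plasma table in SAP 4.2.8.7 for concordance only.

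The cost is about one additional table. The central laboratory reports a result for each sample passing quality control (Protocol 3.3.1), and screening records are already needed for the hazard-ratio weights (SAP 4.2.8.1). The small downside is that screen-failed patients' assay results must be brought into the reporting dataset; the documents do not say whether they are already held there.

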8.2 Sample size estimate

In the 3 tumour biomarker strata A, B, C, for each of the 2 comparisons (ceralasertib + olaparib vs olaparib monotherapy, AZD1775 + olaparib vs olaparib monotherapy), 68 PFS events would have 80% power to show a statistically significant difference at the two-sided 10% significance level if the assumed true treatment effects were HR 0.55. This translates to a 5-month benefit in median PFS over 6 months on olaparib in the *BRCAm* stratum and a 4.17-month benefit in median PFS over 5 months on olaparib in the non *BRCAm* *HRRm* stratum and in the non *HRRm* stratum if PFS is exponentially distributed.

Following the decision of the ISRC to close recruitment to the AZD1775 + olaparib arm, the study will only be sized to detect a difference for the ceralasertib + olaparib vs olaparib monotherapy comparison.

Approximately 50 patients (450 patients overall) will be randomised to each of the 3 treatment arms within each of the 3 biomarker strata so that data maturity for the PFS analysis is approximately 68%. Following the closure of the olaparib+AZD1775 arm in April 2019, fewer than 50 patient per strata will be randomised to this arm and the total number of patients randomised will be lower (approximately 350 patients).

Assuming 15 months non linear recruitment, the required number of PFS events are expected to occur approximately 24 months after the first patient is randomised.

8.3 Definitions of analysis sets

8.3.1 Full analysis set

The full analysis set (FAS) will include all randomised patients with treatment groups assigned in accordance with the randomisation, regardless of the treatment actually received. Patients who were randomised but did not subsequently receive treatment are included in the FAS. The analysis of data using the FAS therefore follows the principles of intent to treat (ITT). All efficacy and **CCI** data will be summarised and analysed using the FAS. Disposition, demographic data, baseline characteristics, etc will be summarized using the FAS.

8.3.2 Safety analysis set

The safety analysis set will include all patients who received at least one dose of randomised treatment (regardless of whether that was the randomised therapy intended or indeed whether, in rare cases, they received therapy without being randomised), according to the treatment they actually received (the detailed definition of “treatment received” will be included in the SAP). All safety data will be summarised and analysed using the safety analysis set. Drug exposure will be summarized using the safety analysis set.

8.3.3 PK analysis set

All patients who received at least one dose of study treatment per the protocol and for whom there is at least one reportable PK concentration will be included in the PK analysis set.

8.4 Outcome measures for analyses

8.4.1 Primary outcome measure (Calculation or derivation of efficacy variables)

Blinded Independent Central Review of RECIST based assessments

The BICR of radiological imaging data will be carried out using RECIST version 1.1. All radiological scans for all patients (including those at unscheduled visits, or outside visit windows) will be provided to the BICR. The imaging scans will be reviewed by two independent radiologists using RECIST 1.1 criteria and will be adjudicated if required. The independent reviewers will be blinded to study treatment. BICR data will be used to determine the endpoints PFS, objective response, DoR, and tumour change for primary and secondary analyses.

For each visit, patients will be programmatically assigned a RECIST 1.1 visit response of CR, PR, SD or PD depending on the status of their disease compared with baseline and previous assessments. If a patient has had a tumour assessment, which cannot be evaluated, then the patient will be assigned a visit response of not evaluable (NE) (unless there is evidence of progression in which case the response will be assigned as PD).

Further details of the BICR will be documented in the BICR Charter.

Investigator RECIST based assessments

From the Investigators review of the imaging scans, the RECIST tumour response data will be used to determine each patient's visit response according to RECIST version 1.1. It will be used to determine the endpoints PFS, objective response, DoR, and tumour change for sensitivity analyses.

At each visit, patients will be programmatically assigned a RECIST 1.1 visit response of CR, PR, SD or PD depending on the status of their disease compared with baseline and previous assessments. If a patient has had a tumour assessment, which cannot be evaluated, then the patient will be assigned a visit response of NE (unless there is evidence of progression in which case the response will be assigned as PD).

Please refer to [Appendix F](#) for the definitions of CR, PR, SD and PD.

PFS

Progression free survival is defined as the time from randomisation until the date of objective disease progression or death (by any cause in the absence of progression) regardless of whether the patient withdraws from randomised therapy or receives another anti-cancer therapy prior to progression. Patients who have not progressed or died at the time of analysis will be censored at the time of the latest date of assessment from their last evaluable RECIST assessment.

However, if the patient progresses or dies after two or more missed visits, the patient will be censored at the time of the latest evaluable RECIST assessment. If the patient has no evaluable visits or does not have baseline data they will be censored at 0 days unless they die within two visits of baseline: in such a case, the death date will be used as the event date.

The PFS time will always be derived based on scan/assessment dates, not visit dates.

RECIST assessments/scans contributing towards a particular visit may be performed on different dates. The following rules will be applied:

Date of progression will be determined based on the earliest of the dates of the component that triggered the progression.

When censoring a patient for PFS, the patient will be censored at the latest of the dates contributing to a particular overall visit assessment.

ORR

The ORR will be defined using the BICR data to define a visit response of CR or PR, with the denominator defined as subset of all randomised patients with measurable disease at baseline per BICR. For sensitivity analysis, ORR is defined as the percentage of patients with at least

one Investigator-assessed visit response of CR or PR and will be based on a subset of all randomised patients with measurable disease at baseline per the site Investigator.

Data obtained up until progression, or last evaluable assessment in the absence of progression, will be included in the assessment of ORR. Patients who discontinue randomised treatment without progression, receive a subsequent anti-cancer therapy (note that for this analysis radiotherapy is not considered a subsequent anti-cancer therapy) and then respond will not be included as responders in the ORR.

DoR

The DoR will be defined as the time from the date of first documented response according to BICR data until date of documented progression according to BICR data or death in the absence of disease progression (ie, date of PFS event or censoring – date of first response + 1). The end of response should coincide with the date of progression or death from any cause used for the PFS endpoint. The time of the initial response will be defined as the latest of the dates contributing towards the first visit response of PR or CR.

For sensitivity analysis, DoR is defined as the time from the date of first documented response according to Investigator assessment until date of documented progression according to Investigator assessment or death in the absence of disease progression (ie, date of PFS event or censoring – date of first response + 1).

If a patient does not progress following a response, then their DoR will use the respective PFS censoring time.

Tumour size change

Absolute change and percentage change from baseline in TLs tumour size at 16 weeks will be based on RECIST TLs measurements taken at baseline and at Week 16. Tumour size is the sum of the longest diameters of the TLs. Baseline for RECIST is defined to be the last evaluable assessment prior to randomisation.

The percentage change in TL tumour size at Week 16 will be obtained for each patient taking the difference between the sum of the TLs at Week 16 and the sum of the TLs at baseline divided by the sum of the TLs at baseline times 100 (ie $(\text{Week 16} - \text{baseline})/\text{baseline} * 100$).

The absolute change in TL tumour size at Week 16 will be obtained for each patient by the difference between the sum of the TL at Week 16 and the sum of the TLs at baseline.

Handling of missing data will be described in the SAP.

OS

Overall survival is defined as the time from the date of randomisation until death due to any cause. Any patient not known to have died at the time of analysis will be censored based on the last recorded date on which the patient was known to be alive.

Note: Survival calls will be made in the 2 weeks following the date of the data cut-off for each OS analysis, and if patients are confirmed to be alive, or if the death date is post the final data cut-off date, these patients will be censored at the date of the final data cut off. Death dates may be found by checking publicly available death registries.

CCI

CCI will be described in the SAP.

Non Progressive Disease (Futility Interim only)

NPD will be assessed 8 weeks after dosing and is defined as the proportion of all patients dosed that have a visit response of SD, PR or CR at Week 8. Earlier visit responses of CR, PR that become PD at Week 8 or NE responses at Week 8 do not constitute NPD at 8 weeks.

A time window around the Week 8 visit will be applied, such that any visits occurring 7 weeks or more after dosing are acceptable; however, if an earlier visit is defined as PD then the visit response at Week 8 would also be defined as PD. If the Week 8 response is missing or NE but the next evaluable response is SD or better then the patient will be defined as having NPD at 8 weeks.

